# History of Protocol Versions:

Version	Date	Sections Changed	Rationale for the Change
1.0	April 26, 2023	N/A	N/A
2.0	May 30, 2023	5.2 inclusion criteria 5.4 payment plan 6.4 storage in lockbox 7.4 patient safety	IRB comment response
3.0	June 6, 2023	5.4 payment plan	
4.0	September 12, 2023	Various	Update consistency with MOP DSMB edits
5.0	September 22, 2023	1 5.2	Study population clarification Updated inclusion wording
6.0		Protocol Overview Section 4	Updated wording for clarity  Revised wording to make timing of assessments clearer
		Section 5.2	Revised inclusion criteria to clarify only cesarean delivery, removal of neuraxial morphine restriction as it is not germane to the primary study objectives, specified term delivery definition
	December 7, 2023	Section 5.3	Revised exclusion criteria to clarify patient undergoing general anesthesia to match wording in other documents; other wording modification to match wording in institutional protocol; removed contraindication to NSAID as it is not germane to primary study objective

		Section 7.1	Updated screening procedures to reflect workflow optimization
		Section 7.6	Corrected a spelling error
		Section 8.2	Deleted "risks of withholding breastfeeding for 60 hours" as we are not asking women to withhold breastfeeding
		Section 9.2	Spelling error
7.0		Appendix 3	Corrected to include protocollisted assessments at postpartum week 12, which is Day 84, Visit 13
		Appendix 2	Corrected RASS and vital signs to line up with protocol text LSD >8 cutoff for PI notification and bedside check to enhance safety and facilitate direct event attributions
	May 16, 2024	Figure 1	Corrected to line up with protocol text for RASS, side effect assessments and postpartum assessments
		Section 3.4.1, 6.3, Table 1 of Section 6.2	DLT event definition revised to include complete infusion cessation due to intolerable side effect acceptability ratings by patient. Table now specifies events that qualify as DLT in accordance with revised DLT definition

Section 6.2	Added grace period range +15 minutes for maintenance infusion dose adjustment times
Sections 3.4.1, 6.3, 9.1, 12.3, Table 1 of Section 6.2	Reduced systolic blood pressure cutoff from 190mmHg to 160mmHg in accordance with DSMB recommendations and to be more aligned with systolic blood pressure cutoffs in the pregnant and postpartum population
Section 6.6	Clarified rescue medication protocol for nausea/vomiting

Appendix 2 – Schedule of Perinatal, Surgical, and Infusion-Specific Research Activities	
Appendix 3 – Schedule of Postpartum Research Activities	

# **ABBREVIATIONS AND ACRONYMS**

AE	Adverse Event	
ADL	Activities of Daily Living	
ASA PS	American Society of Anesthesiologist Physical Status	
AUC	Area Under Curve	
CD	Cesarean Delivery	
CFR	Code of Federal Regulations	
Cmax	Peak concentration of "drug"	
CRF	Case Report Form	
Css	Concentration of "drug" at Steady State	
DHHS	Department of Health and Human Services	
DLT	Dose Limiting Toxicity	
DSMB	Data Safety Monitoring Board	
EPDS	Edinburgh Postnatal Depression Scale	
FDA	Food and Drug Administration	
GCP	Good Clinical Practice	
HIPAA	Health Insurance Portability and Accountability Act	
IB	Investigator's Brochure	
ICH	International Conference on Harmonization	
IDE	Investigational Device Exemption	
IDS	Investigational Drug Service	
IND	Investigational New Drug Application	
IRB	Institutional Review Board	
ITT	Intention-To-Treat	
IV	Intravenous	
MDD	Major Depressive Disorder	
MTD	Maximum Tolerate Dose	
NCT	National Clinical Trial	
NIH	National Institutes of Health	
NMDA	N-Methyl-D-Aspartate Receptor	
PCP	Phencyclidine	
PD	Pharmacodynamics	
PI	Principal Investigator	
PK	Pharmacokinetic	
PPD	Postpartum Depression	
PSS	Perceived Stress Scale	
RASS	Richmond Agitation Sedation Scale	
REDCap	HIPAA compliant data management software	
RID	Relative Infant Dose	
SAE	Serious Adverse Event	
SSRI	Selective Serotonin Reuptake Inhibitor	
UPMC	University of Pittsburgh Medical Center	

# 1 Protocol Overview

Study Description	The purpose of this study is to identify a tolerable dose for postpartum ketamine infusion using a maximum tolerated dose (MTD) 3+3 design. A loading dose over 1 hour will be the MTD variable to be tested, as our data suggest that ketamine side effects occur with the loading dose.
Study Population:	Patients having cesarean delivery (CD) who are either: 1) planning not to breastfeed; or 2) are receiving ketamine as part of clinical care, will be enrolled. Ketamine will be started in postpartum patients, after cord clamping.
Planned Sample Size:	The projected sample size will be a maximum of 12 patients with complete primary outcome data within the MTD 3+3 design.
Participating Institutions (if a multicenter clinical trial)	N/A

# 1.1 Study Schema

Figure 1. Assessment timeline for MTD study and follow-up assessments

[figure not shown]
[figure not shown]

Figure 2. MTD dosing schematic for PREPARE 1.

# 2 Background and Rationale

# 2.1 Background

A lack of data on new pain treatments in pregnancy and lactation puts 1.2 million US women having cesarean delivery (CD) every year at risk for poor pain control, depressed mood, and poor recovery. Despite high individual variability in pain after CD, current CD treatments ignore the multidimensionality of pain, including the influence of mood on pain. NMDA receptor antagonists like ketamine significantly reduce postoperative pain and opioid use by up to 40%. In addition to its analgesic effects, a single dose of IV ketamine has been shown to rapidly reduce depressive symptoms by 50% and remission rates 43-77% in non-obstetric populations. Evidence of successful post-surgical pain management and rapid reduction of depressive symptoms render ketamine a great candidate for post-CD pain management and potential reduction of PPD symptomology.

Ketamine at sub-anesthetic doses is effective in post-surgical acute pain management, with long-lasting analgesia. Many trials (non-obstetric) have shown ketamine effectiveness for post-operative analgesia $^{94.96}$ . Available postpartum ketamine studies have focused on various doses (ranging 0.1-0.5 mg/kg, single doses, infusions) for efficacy $^{16-18,66}$ , but have not emphasized side effects. Although high doses of ketamine induce psychomimetic effects, low doses, such as in the current proposal, can reduce pain without side effects $^{10,78}$  and potentially reduce pain intensity for 1 year after a single dose (effect size 0.61, 95% CI 0.40 – 0.80) $^{97}$ .

In addition to its analgesic effects, ketamine use for depression treatment promotes fast, effective depression symptom reductions, a robust effect occurs from 4-72 hours post-infusion (0.5 mg/kg over 40 min) in patients with MDD; this dose is commonly used for depression. The antidepressant effect lasts beyond psychotomimetic symptoms, which peak during the infusion and return to baseline within 1-2 hours. These findings contrast traditional antidepressants whereby only 1/3 of patients become symptom-free after 7 weeks of treatment with SSRI. A widely cited trial of 205 ketamine doses (0.5mg/kg, 40 min) for depression concluded ketamine was, "safe and well- tolerated" but did not probe patient acceptability of side effects. Dose-dependent side effects are common, with a high incidence of vertigo, nausea, sedation, and dissociation in intranasal dosing to plasma levels similar to an IV dose of 0.5 mg/kg over 40min. These dose-dependent side effects preclude widespread use in the peripartum population. Identifying ketamine dose tolerability in a post-CD population has the potential to improve treatment of postoperative pain as well as mood-related outcomes of chronic pain such as comorbid onset of PPD. This work will

Defining postpartum ketamine PK is critical to understanding the potential role of ketamine for PPD prevention, and to understanding the plasma ketamine concentration time profile with its maximum tolerated dose. There are no PK/PD models for ketamine-induced side effects or analgesia, although there are isolated reports of ketamine side effects with plasma concentrations. Available trials that conclude ketamine is "well tolerated" did not query patient perspectives in acceptability. The duration of ketamine exposure may be important as well, given that subcutaneous administration may have greater antidepressant duration than intravenous administration of the same dose, despite lower

peak plasma concentrations in subcutaneous administration. These knowledge gaps are significant because they limit patient-centered acceptability of ketamine and a finer understanding of its potential effective utility for PPD prevention. Because ketamine is metabolized by CYP3A and CYP2B6 (increased activity in pregnancy and immediately after delivery), and because pregnancy induces sensitivity to anesthetics, it is critical in this project to identify a tolerable dose of postpartum ketamine and the perioperative factors impacting its PK.

#### 2.2 Rationale

Defining postpartum ketamine tolerable doses and ketamine PK is critical to understanding the potential role of ketamine for PPD prevention, and to understanding the plasma ketamine concentration time profile with its maximum tolerated dose. There are no PK/PD models for ketamine-induced side effects or analgesia, although there are isolated reports of ketamine side effects with plasma concentrations. Available trials that conclude ketamine is "well tolerated" did not query patient perspectives in side effect acceptability. The duration of ketamine exposure may be important as well, given that subcutaneous administration may have greater antidepressant duration than intravenous administration of the same dose, despite lower peak plasma concentrations in subcutaneous administration. These knowledge gaps are significant because they limit patient-centered acceptability of ketamine and a finer understanding of its potential effective utility for PPD prevention. Because ketamine is metabolized by CYP3A and CYP2B6 (increased activity in pregnancy and immediately after delivery), and because pregnancy induces sensitivity to anesthetics, it is critical in this project to identify a tolerable dose of postpartum ketamine and the perioperative factors impacting its PK.

# 3 Hypotheses, Objectives and Endpoints

# 3.1 Hypotheses

# 3.2 Primary Hypothesis

The purpose of this study is to identify a tolerable dose for postpartum ketamine infusion using a maximum tolerated dose (MTD) 3+3 design. A loading dose over 1 hour will be the MTD variable to be tested, as our data suggest that ketamine side effects occur with the loading dose.

Our working hypothesis, based on our preliminary PK and safety data and that of Loo et al [19], is that a 12-hr IV ketamine infusion of 0.05 mg/kg/hour is the MTD.

# 3.3 Objectives

#### 3.3.1 Primary Objective:

Quantify maximum tolerable dose of postpartum ketamine infusion post-cesarean delivery.

# 3.3.2 Secondary Objective

Quantify *side effect* acceptability of low-dose ketamine infusion in peripartum people.

### 3.3.3 Exploratory Objectives

Measure maternal pain and depression in this cohort before and after cesarean delivery until 12weeks postpartum.

# 3.4 Endpoints

# 3.4.1 Primary Endpoint

Maximum Tolerated Dose (MTD). The MTD will be defined as the dose at which fewer than 33% of patients experience a DLT defined by intolerability.

Tolerability (dichotomous Yes/No)

Tolerability (YES) will be defined as: lack of adverse events (adverse event defined as: severe unresolved hemodynamic effect: systolic blood pressure <80 or >160, heart rate <40 or >120).

Lack of Tolerability will be defined as presence of any adverse event (i.e., severe unresolved hemodynamic effect: systolic blood pressure <80 or >160, heart rate <40 or >120).

A **DLT** event is defined by complete infusion cessation due to intolerable side effect acceptability ratings by patient, OR the experience of an intolerable event as defined above. The escalation of dosing will be as noted in Figure 2 and is based on a modified Fibonacci sequence  $^{101,102}$  with smaller proportional increases in dose in the escalation scheme. Escalations occur until 2 in a cohort of 3 to 6 experiences DLT (i.e., until  $\geq$ 33% of patients experience DLT at that dose). The dose **below** this level estimates the MTD.

Participants will be classified as having had a DLT if any of the following conditions are met:

- Persisting (i.e., unresolved after 3 consecutive measurements within a 15-minute interval)
  hemodynamic side effects defined as below and despite treatments or minimizing
  infusion rates as specified.
  - Systolic blood pressure <80 or >160
  - Heart rate <40 or >120
- Complete infusion cessation due to intolerable side effect acceptability ratings by patient

Primary Outcomes will be measured at a minimum of every 4-hours from the start of the ketamine infusion (t = 0) for 24-hours (12-hours post infusion cessation). Additional assessments will be administered between the 4-hour measurements if any adverse event or side effect is noted by the patient.

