# Events that Trigger Dose Adjustment Procedures:

- Persisting unresolved hemodynamic side effects defined as Systolic blood pressure <80 or >160,
   Heart rate <40 or >120^33
  - o Unresolved after 3 consecutive measurements within a 15-minute interval
- Persisting (i.e., unresolved within 1 hour of onset) side effects sedation, dizziness, lightheadedness, persistent itchiness, bad dreams, hallucinations, or other side effects that are reported as not acceptable to patients or clinicians, despite minimizing infusion rate.
- Table 1 includes procedures for dose adjustments.

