#### 10.1 Severity

The severity of adverse changes in physical signs or symptoms will be classified as follows:

- *Grade 1 (Mild):* asymptomatic or mild symptoms; clinical or diagnostic observation only; intervention not indicated.
  - e.g., sedation, dizziness, lightheadedness, bad dreams, hallucinations, euphoria, dysphoria, nausea, vomiting
- *Grade 2 (Moderate):* minimal, local, or noninvasive intervention indicated; limiting ageappropriate ADL.
  - o e.g., dysphoria, vomiting
- *Grade 3 (Severe):* medically significant but not immediately life-threatening; hospitalization or prolongation of hospitalization indicated; disabling; limiting self-care/ADL.
  - o e.g., hypertensive urgency or emergency requiring escalated or inpatient treatment
- *Grade 4 (Life-threatening):* consequences; urgent intervention indicated.
  - o e.g., stroke from uncorrected severe hypertension

• *Grade 5 (Death):* event is a direct cause of death.

An independent DSMB will define frequency of monitoring of the tolerability and DLT data.

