# 10.4 Reporting Serious Adverse Events

If there is a suggestion that any research procedures have resulted in an injury to subjects, there will be immediate contact with the Principal Investigator who is listed on the first page of the informed consent documents. Any SAE, which is determined by the PI to be unexpected and at least possibly related to study intervention, will be reported to the IRB as soon as possible. The PI is responsible for notifying the FDA within required timeframes. The IDSMB will be notified in writing at the soonest possible timepoint that the event has been identified. The IRB and FDA and will include all known details regarding the nature of the SAE. Outcomes of SAEs not previously reported will be reported to the PI, IRB and FDA via a follow-up report.

Life-threatening or fatal unexpected adverse events associated with the use of the study drug or procedures must be reported to the IRB within 24 hours of discovery of the incident with subsequent follow-up submission of a detailed written report. The IDSMB and IRB will be notified by telephone or facsimile transmission of a human adverse event that is fatal or life-threatening no later than 7 calendar days after receiving the respective human adverse event information, followed by the subsequent submission of a written IND Safety Report. Serious and unexpected adverse events associated with the use of the study drug or procedures will be reported to the IRB with subsequent follow-up submission of a detailed written report in accordance with the respective policies and procedures of the IRB. A summary report of the findings will be prepared and submitted to the regulatory agencies. A written IND Safety Report (i.e., Form FDA 3500A) will be submitted to the FDA as soon as possible and, in no event, later than 15 calendar days following the investigator-sponsor's receipt of the respective adverse event information.

A summary of the SAEs that occurred during the previous year will be included in the FDA annual progress report as well as in the annual IRB continuing review.

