# Withdrawal of Subjects due to Adverse Events

Participants will be withdrawn if they experience a life-threatening adverse event, inpatient hospitalization or prolongation of existing hospitalization, a persistent or significant incapacity or substantial disruption of the ability to conduct normal life functions, or other important medical events that may not result in death, be life threatening, or require hospitalization may be considered serious when, based upon appropriate medical judgment, they may jeopardize the patient, or subject, and may require medical, or surgical intervention to prevent one of the serious outcomes listed above.

DSMB will review all events pertaining to participant withdrawals. An independent decision will be made regarding trial discontinuation based on risk assessment for current and future trial participants.

Withdrawn participants will be replaced at a proportion of 1:1. Procedures are as follows:

- Study personnel, investigators, and pharmacy will be informed of the need for replacement due to participant withdrawal.
- Subsequent data to be collected from the withdrawn participant will be restricted to the
  minimum amount necessary to continue to monitor safety, i.e., side effect diary including
  questions of sedation, LSD short form, dizziness, lightheadedness, bad dreams, nausea,
  vomiting, pruritus, hallucinations.

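### The DLT definitions disagree, and the plan does not say whether a patient withdrawn for a serious drug-related event stays in the 3+3 count

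*Combined protocol and SAP*

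**What the plan says.** Section 3.4.1 gives the rule in running text and again as a list. The text offers two routes to a DLT. One is "complete infusion cessation due to intolerable side effect acceptability ratings by patient"; the second is an event that the section classes as intolerable. The intolerable event meant there is hemodynamic only: "adverse event defined as: severe unresolved hemodynamic effect: systolic blood pressure <80 or >160, heart rate <40 or >120". The list repeats the same two routes and no others. The count then drives the design: "Escalations occur until 2 in a cohort of 3 to 6 experiences DLT", equated with 33% or more, and the dose below that level estimates the MTD.

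Three other places define or describe the same thing:

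- Section 12.3 repeats the hemodynamic definition, calls it a serious adverse event, and does not mention cessation because of patient ratings.
- Table 1 (Section 6.3) marks as DLTs, in its last column, the hemodynamic and patient-rated events. It also marks unresolved RASS of -2 or below or respiratory rate under 8, and unresolved nausea or vomiting. The last two rows need no patient rating.
- The opening of Section 12 describes DLT as unacceptable side effects or adverse events, without limiting the latter to hemodynamics.

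Section 6.3 lets dose adjustment be triggered by "other side effects that are reported as not acceptable to patients or clinicians". Section 10.1 grades events 1 to 5, with Grade 3 described as "medically significant but not immediately life-threatening; hospitalization or prolongation of hospitalization indicated". Under Section 11.1, "Participants will be withdrawn if they experience a life-threatening adverse event, inpatient hospitalization or prolongation of existing hospitalization" (among other serious outcomes), and withdrawn participants are replaced 1:1. None of these sections says that a grade or a serious outcome makes an event a DLT.

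**The concern.** The DLT definition is both the primary endpoint and the escalation rule, so two people applying the plan to the same patient should reach the same tally. They may not, for three reasons.

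1. Whether a sedation, respiratory or antiemetic-resistant event is a DLT depends on whether one reads Section 3.4.1 or Table 1.
2. Some events have no stated status anywhere: a drug-related Grade 3 to 5 event or Section 11.1 outcome that is not hemodynamic, not in Table 1 and not rated by the patient; and an infusion stopped at investigator discretion at one of the earlier Table 1 steps.
3. A patient with a serious event is withdrawn and replaced, and nothing says that she stays in the numerator and denominator.

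At stake is the reported MTD. With at most six patients per level, one patient decides between stopping and escalating.

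**Working it through.** **Side by side**

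| Event | 3.4.1 | Table 1 | 12 (opening) | 12.3 |
|---|---|---|---|---|
| Persisting SBP/HR effect | DLT | DLT | covered | covered |
| Cessation because of patient ratings | DLT | DLT in last column | covered | not mentioned |
| Unresolved RASS -2 or below, or respiratory rate <8 | not listed | DLT in last column | arguably | not mentioned |
| Unresolved nausea or vomiting, no patient rating | not listed | DLT in last column | arguably | not mentioned |
| Discretionary stop at an earlier Table 1 step | only if due to patient ratings | no label | unclear | not mentioned |
| Other related Grade 3-5 or 11.1 event | not listed | not listed | arguably | not mentioned |

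The gap for early stops is plainest in the sedation and respiratory row. If the investigator stops the infusion when there is no resolution within 1 hour, that cell carries no DLT label and Section 3.4.1 does not cover it. The same event carried to the last column is a DLT.

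**Who is in the cohort.** The Protocol Overview sizes the trial by patients with complete primary outcome data. Section 4 delays the first escalation decision until three patients complete the first dose level. After a Section 11.1 withdrawal, the data still collected are diary-type side-effect items; vital signs, the basis of the hemodynamic DLT, are not among those named. Together these favour tallying the replacement instead of the withdrawn patient, though no sentence says so.

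**The plan's own threshold.** 2/6 = 33.3%, which reproduces the stated 33%; 1/6 = 16.7%.

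**One cohort.** Take six patients at a level, one with a listed DLT and one with a related serious event outside the list. If both count, the tally is 2/6 = 33.3%: stop. If the second is withdrawn and her replacement has no DLT, it is 1/6 = 16.7%: escalate.

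**Size under assumed rates.** Let c be the rate of listed DLTs and u the rate of related serious events outside the list, taken as not overlapping. The documents give neither, so both are assumptions. Escalation needs 0/3, or 1/3 followed by 0/3:

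P(escalate) = (1-p)³ + 3p(1-p)² × (1-p)³

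with p = c + u if all events count; p = c if the patient is kept but her event is not a DLT; and p = c/(1-u) if she is withdrawn and replaced.

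For c = 15%, u = 18%:
- All counted, p = 0.33: 0.301 + 0.134 = 0.434.
- Replaced, p = 0.15/0.82 = 0.183: 0.545 + 0.200 = 0.745.

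| c | u | All counted | Kept, not a DLT | Withdrawn and replaced |
|---|---|---|---|---|
| 10% | 10% | 0.709 | 0.906 | 0.887 |
| 10% | 20% | 0.494 | 0.906 | 0.862 |
| 20% | 10% | 0.494 | 0.709 | 0.660 |
| 20% | 20% | 0.309 | 0.709 | 0.600 |
| 15% | 18% | 0.434 | 0.814 | 0.745 |
| 0% | 33% | 0.434 | 1.000 | 1.000 |

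The direction is the same in every row. The loss comes from not counting the event: keeping the patient as a non-DLT is no better than replacing her. A statement on the denominator alone would therefore not repair the rule.

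**The case against.** A reader might infer that every event other than a hemodynamic or patient-rated one escapes the count. The documents do not support that. Table 1 makes unresolved sedation, low respiratory rate, nausea and vomiting DLTs without a patient rating, the version history says the table specifies which events qualify, and Section 12 uses broader wording. Those events are the subject of a contradiction between sections, not of a uniform omission.

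A reader might also infer that any patient whose infusion a clinician stops is withdrawn and replaced. That joins two separate rules. A Table 1 stop leads to monitoring under Sections 7.4 and 7.5; for adverse events, 1:1 replacement is written for the serious outcomes in Section 11.1.

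Third, non-counting of a withdrawn patient is inferred from silence. A patient who meets a listed condition is classified as a DLT, and nothing says withdrawal reverses that. Figures 2 and 3 are not visible in the text available and may hold counting detail. This stands as a limit: the plan permits the lower tally but does not order it. It does not help a patient whose event is not on any list.

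Fourth, the practical reach may be small. The protocol's own Grade 3 and 4 examples are hypertensive and would often meet the blood-pressure limit; acceptability ratings are collected after any adverse event up to 24 hours (Appendix 2, note b); Section 8.1 rates the foreseeable drug effects mild to moderate; and the DSMB reviews all withdrawals and can end the trial. All of this is fair. But board review is not an entry in the 3+3 tally, and the MTD is estimated from the tally.

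**Conclusion.** The point holds as a contradiction plus a gap. Sections 3.4.1, 12 and 12.3 and Table 1 give different DLT definitions. Earlier discretionary stops outside the patient-rated route, and related serious events outside the listed categories, have no stated status. Section 11.1 does not say whether a withdrawn patient stays in the count. Followed as written, a level can be recorded as 1/6 and escalated where counting every related serious event gives 2/6 and a stop.

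The direction is certain if any such event occurs and is left out; the size is not. The probabilities rest on assumed rates of 0 to 20% for listed DLTs and 10 to 33% for unlisted events, with no overlap and with every unlisted event judged related. They illustrate and do not predict. The documents do not show that the worst events are generally invisible to the escalation rule, and that should not be claimed. Because the ambiguity sits in the primary endpoint and is cheap to remove, it should be corrected.

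**What to change.** Three changes of wording, all about what is counted and none about how a patient is treated:

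1. Reconcile Section 3.4.1, Table 1, Section 12 and Section 12.3 into one DLT definition for the escalation count. It should include the events Table 1 already labels as DLTs, and any adverse event of Grade 3 or higher (Section 10.1) or Section 11.1 outcome judged at least possibly related (Section 10.2). Section 12.3 should refer to that definition and not redefine a serious adverse event.
2. State whether an infusion stopped by a clinician for a drug effect at an earlier Table 1 step counts as a DLT.
3. State in Section 11.1 that a patient withdrawn for a drug-related event stays in the DLT numerator and denominator at her assigned level, and that 1:1 replacement applies only to withdrawals without a DLT. Make the Protocol Overview and Section 4 agree on who is evaluable.

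Grades and relatedness are already collected, so no new data are needed. The cost is a more conservative MTD. At the assumed c = 10% and u = 10%, the chance of stopping a level rises from 1 - 0.887 = 0.113 to 1 - 0.709 = 0.291. The possibly related category also admits events to which other factors contributed, such as the surgery or the spinal medication. The team should accept that cost explicitly or justify a stricter relatedness threshold.
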